**Table 2: Construction of Analysis Time point and Visit Window**

Analysis phase	Analysis period	Target daya	Analysis time point (numeric version)	Analysis time point	Time interval (days)b
Screening		$-\infty$	-1	Screening	<0
Treatment	Initial Treatment	1	0	Baseline	Pre-dose
		7	1	Week 1	[2,11]
		14	2	Week 2	[12,21]
		28	4	Week 4	[22,42]
		56	8	Week 8	[43,70]
		84	12	Week 12	[71, 98]
		112	16	Week 16	[99, 126]
		140	20	Week 20	[127, 154]
		168	24	Week 24	[155, 182]
	Treatment Extension	196	28	Week 28	[183, 210]
		224	32	Week 32	[211, 238]

		252	36	Week 36	[239, 266]
		280	40	Week 40	[267, 294]
		308	44	Week 44	[295, 322]
		336	48	Week 48	[323, $+\infty$ ]
	last visit in treatment phase		49*	EOT	
Follow-up		9	50	Follow-up Week 2	[1,16]
		23	52	Follow-up Week 4	[17,30]
		37	54	Follow-up Week 6	[31,44]
		51	56	Follow-up Week 8	[45,65]
		79	60	Follow-up Week 12	[66,93]
		107	64	Follow-up Week 16	[94,121]
		135	68	Follow-up Week 20	[122,149]
		163	72	Follow-up Week 24	[150,191]
		219	80	Follow-up Week 32	[192,247]
		275	88	Follow-up Week 40	[248,303]
		331	96	Follow-up Week 48	[304, $+\infty$ ]
Overall		last visit in the study	999*	EOS	

a Target day in follow-up phase equals target day in the protocol minus 5 days.

b The reference day of the Treatment and Screening phase is the day of the first study agent intake (= day 1 in Treatment phase). The reference day of the Follow-up phase is the first day of the follow-up phase.

\*End of treatment and End of study visit (last available data at the end of the study) will be derived

The number of days in the treatment phase (ADY) will be defined as:

$ADY = \text{visit date} - \text{date of first study drug intake} + 1$  for visits on or after the day of first study drug intake

$ADY = \text{visit date} - \text{date of first study drug intake}$  for visits before the day of first study drug intake

The number of days in the follow-up phase (ADY) will be defined as:

$ADY = \text{visit date} - \text{start date of the follow-up phase} + 1$

All visits (regardless the investigated parameter) will be allocated within each phase/period to analysis time points based on the number of days in phase (ADY)

If two visits fall within the same interval only one measurement will be selected for the descriptive statistics/tabulations per time point and graphics in order to have only one evaluation per subject per analysis time point. Following rules will be applied:

- The measurement closest to the target day will be used.
- If the measurements fall equidistant from the target day, the last measurement in time within the interval will be used

---

- If there are two measurements on the same day and time, then the measurement with the highest sequence number or group ID (e.g. ECG measurements) will be used.

The listings will include all measurements.

End of treatment (i.e. EOT) and end of study (i.e. EOS) time points will be included in all analysis over time unless stated otherwise.

Note: For the selection of the PRO measurements the above algorithm needs to be performed on the entire questionnaire (filled in at a specific date and time) and not on the individual questions (i.e., not mixing answers from different questionnaires)

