### 5.2.1.1 Mixed effects model for repeated measures

The main comparisons of interest in the efficacy analyses are:

- to evaluate the efficacy of 24 weeks of JNJ-56136379 monotherapy versus placebo+NA;
- to evaluate the efficacy of 24 weeks of JNJ-56136379+NA versus placebo+NA;
- to evaluate the efficacy of 24 weeks of JNJ-56136379 monotherapy versus JNJ-56136379+NA.

The primary endpoint, Week 24 HBsAg change from baseline, will be analyzed by a comparison of each dose of JNJ-56136379 added to the background NA therapy with the concurrent control arm (placebo + NA), within each of the 4 categories defined by subject population and HBeAg status:

- Low dose (75 mg) of JNJ-56136379+NA with placebo+NA (Part A) in currently not treated HBeAg positive subjects
- Low dose (75 mg) of JNJ-56136379+NA with placebo+NA (Part A) in currently not treated HBeAg negative subjects
- Low dose (75 mg) of JNJ-56136379+NA with placebo+NA (Part A) in virologically suppressed HBeAg positive subjects
- Low dose (75 mg) of JNJ-56136379+NA with placebo+NA (Part A) in virologically suppressed HBeAg negative subjects
- High dose (TBD) of JNJ-56136379+NA with placebo+NA (Part B) in currently not treated HBeAg positive subjects
- High dose (TBD) of JNJ-56136379+NA with placebo+NA (Part B) in currently not treated HBeAg negative subjects
- High (TBD) of JNJ-56136379+NA with placebo+NA (Part B) in virologically suppressed HBeAg positive subjects

---

- High (TBD) of JNJ-56136379+NA with placebo+NA (Part B) in virologically suppressed HBeAg negative subjects

The same comparisons versus placebo+NA as above will also be conducted with JNJ-56136379 monotherapy.

Change from baseline based on log10 transform for quantitative HBsAg, will be analyzed by subject population using mixed effects model for repeated measures [MMRM]) including treatment group, analysis time point (treated as discrete/categorical), their interaction, HBeAg status (in the pooled analysis only), as fixed effects. The covariance structure will include a random intercept at the level of the subject to capture between-subject variability, while within-subject variability will be captured with an unstructured (type=UN) covariance matrix. In case the latter leads to convergence issues, alternative within-subject covariance structures will be considered, in the following hierarchy:

- i) First-order ante-dependence structure (type=ANTE(1)),
- ii) Heterogeneous first-order autoregressive structure (type=ARH(1))

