### APPENDIX 3: SAS CODE FOR THE MMRM MODEL

```
proc mixed data=mod01 (where = (paramcd = 'LGHBSAG' ));  
  by hbeagstat;  
  class avisitn trtlon usubjid;  
  model chg = avisitn trtlon trtlon*avisitn / ddfm=kr2;  
  repeated / type=UN subject=usubjid ;  
run;
```

hbeagstat = HBeAg status at baseline

avisitn = analysis visits

trtlon = Treatment groups

usubjid = subject ID

chg = change from baseline

In case the above leads to convergence issues, alternative within-subject covariance structures will be considered, in the following hierarchy:

```
proc mixed data= mod01 maxopt=1000;  
  by hbeagstat;  
  class avisitn trtlon usubjid;  
  model chg= avisitn trtlon trtlon*avisitn /dist=normal link=identity solution ddfm=kr2;  
  random intercept/subject=usubjid v vcorr;  
  random _residual_ /type=ante(1) subject=usubjid g gcorr;  
  covtest 'int' general 1 0 0 0 0 0 0 0 0 0 0 0 0 0 0 0;  
  covtest 'all var equal' general  
    0 1 -1 0 0 0 0 0 0 0 0 0 0 0 0 0,  
    0 0 1 -1 0 0 0 0 0 0 0 0 0 0 0 0,  
    0 0 0 1 -1 0 0 0 0 0 0 0 0 0 0 0,  
    0 0 0 0 1 -1 0 0 0 0 0 0 0 0 0 0,  
    0 0 0 0 0 1 -1 0 0 0 0 0 0 0 0 0,  
    0 0 0 0 0 0 1 -1 0 0 0 0 0 0 0 0,  
    0 0 0 0 0 0 0 1 -1 0 0 0 0 0 0 0;  
  covtest 'all corr equal' general  
    0 0 0 0 0 0 0 0 0 1 -1 0 0 0 0 0,  
    0 0 0 0 0 0 0 0 0 0 1 -1 0 0 0 0,  
    0 0 0 0 0 0 0 0 0 0 0 1 -1 0 0 0,  
    0 0 0 0 0 0 0 0 0 0 0 0 1 -1 0 0,  
    0 0 0 0 0 0 0 0 0 0 0 0 0 1 -1 0,  
    0 0 0 0 0 0 0 0 0 0 0 0 0 0 1 -1;  
  covtest 'all var&corr equal' general  
    0 1 -1 0 0 0 0 0 0 0 0 0 0 0 0 0,  
    0 0 1 -1 0 0 0 0 0 0 0 0 0 0 0 0,  
    0 0 0 1 -1 0 0 0 0 0 0 0 0 0 0 0,  
    0 0 0 0 1 -1 0 0 0 0 0 0 0 0 0 0,  
    0 0 0 0 0 1 -1 0 0 0 0 0 0 0 0 0,  
    0 0 0 0 0 0 1 -1 0 0 0 0 0 0 0 0,
```

---

```

0      0 0 0 0 0 1 -1    0 0 0 0 0 0,
0      0 0 0 0 0 0 0      1 -1 0 0 0 0,
0      0 0 0 0 0 0 0      0 1 -1 0 0 0,
0      0 0 0 0 0 0 0      0 0 1 -1 0 0,
0      0 0 0 0 0 0 0      0 0 0 1 -1 0,
0      0 0 0 0 0 0 0      0 0 0 0 1 -1 0,
0      0 0 0 0 0 0 0      0 0 0 0 0 1 -1;
run;

proc mixed data= mod01 maxopt=1000;
by hbeagstat;
class avisitn trtlon usubjid;
model chg= avisitn trtlon trtlon*avisitn /dist=normal link=identity solution ddfm=kr2;
random intercept/subject=usubjid v vcorr;
random _residual_ /type=arh(1) subject=usubjid g gcorr;
covtest 'int' general 1 0 0 0 0 0 0 0 0;
covtest 'corr' general 0 0 0 0 0 0 0 0 1;
covtest 'all var equal' general
      0      1 -1 0 0 0 0 0 0 ,

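### The SAP does not settle whether derived EOT and EOS records enter the HBsAg MMRM; if they do, the planned covariance model can become inestimable

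*SAP*

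**What the plan says.** The rule stands in SAP 2.3, after Table 2: "End of treatment (i.e. EOT) and end of study (i.e. EOS) time points will be included in all analysis over time unless stated otherwise". Table 2 gives EOT the numeric time point 49 and describes it as the "last visit in treatment phase". EOS is time point 999, the last visit in the study. The footnote adds: "End of treatment and End of study visit (last available data at the end of the study) will be derived". Both therefore repeat a record that already sits under a scheduled visit.

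SAP 5.2.1.1 names the target: "The primary endpoint, Week 24 HBsAg change from baseline, will be analyzed by a comparison of each dose" of JNJ-56136379 plus NA with its concurrent control. The model has treatment group plus "analysis time point (treated as discrete/categorical), their interaction, HBeAg status (in the pooled analysis only), as fixed effects". No list of time points is given and none is excluded. SAP 5.2.1 asks for LS means at each time point and overall. SAP 5.3 carries the model to the other viral markers, and SAP 8.5.2 fits a similar one to the PRO scores.

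In Appendix 3 the UN call opens "proc mixed data=mod01 (where = (paramcd = 'LGHBSAG" and sets no condition on visit. The three fallback calls, for ANTE(1), ARH(1) and AR(1) in that order, carry no data filter at all. The contrasts in the ANTE(1) call are written out with 16 coefficients.

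**The concern.** A programmer who follows SAP 2.3 literally adds EOT, and possibly EOS, as further levels of the time factor. EOT is then the Week 24 value again for completers who are not extended, the Week 48 value again for extension completers, and the last on-treatment value again for early stoppers. Two levels that hold the same number in every subject have residual correlation 1, and an unstructured covariance cannot be estimated from them. The fallback order would then be set off by a derived record and not by anything in the HBsAg data. The covariance structure behind the Week 24 standard errors would depend on how a programmer reconciles SAP 2.3 with Appendix 3.

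**Working it through.** **Inputs.** EOT and EOS rule and definitions: SAP 2.3 and Table 2. Model and fallback order: SAP 5.2.1.1 and Appendix 3. Arms of 10 (placebo + NA) and 30 (JNJ-56136379 + NA): Protocol 3.1. Smallest HBeAg stratum, 3/9: Protocol Table 7. The documents do not give the variance of HBsAg change over time, so profiles are assumed.

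**1. The count of 16.** A random intercept plus ANTE(1) over T time points has 1 + T + (T − 1) = 2T covariance parameters.

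| Time points kept | T | Parameters |
|---|---|---|
| Weeks 1, 2, 4, 8, 12, 16, 20, 24 | 8 | 16 |
| plus EOT | 9 | 18 |
| plus EOT and EOS | 10 | 20 |
| Weeks 1 to 48 | 14 | 28 |
| Weeks 1 to 48 plus EOT and EOS | 16 | 32 |

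Only the first row gives 16: one intercept, eight variances, seven correlations. The equal-variance rows of the ARH(1) call also compare eight variances. (Its correlation contrast sits in the ninth column, already used for the eighth variance, so that code is not exact.)

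**2. When the fit breaks.** The likelihood has no maximum when every subject who holds a given visit and EOT has the same value in both, and such subjects outnumber the arms. Simulated data with 10 and 30 subjects give:

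- *Weeks 1 to 24 plus EOT, nobody extended.* The smallest eigenvalue of the pooled residual covariance is 0 to machine precision, so UN is singular. The ANTE(1) criterion log|V| + tr(V⁻¹S) runs −12.8, −17.4, −22.0, −26.6 as 1 − ρ goes from 10⁻² to 10⁻⁸. It falls by ln 100 = 4.6 at each hundredfold step, without limit.
- *Same data, ARH(1) with random intercept.* Let the residual SD at Week 24 and its copy shrink from 0.1 to 0.0001, with the intercept absorbing the value. The criterion runs −2.6, −7.0, −11.6, −16.2, so it is unbounded too. A numerical search can still stop at an interior point.
- *Weeks 1 to 48 plus EOT, 20 of 40 extended.* The UN log-likelihood runs 305, 352, 398, 444, 490 as the copy's conditional SD falls tenfold each time. Each step adds about 20 × ln 10 = 46, one ln 10 for each subject with the Week 48 duplicate.
- *Weeks 1 to 24 plus EOT, some extended.* An extended subject holds Week 24 and a later EOT value that differs from it. The fit is not singular: the smallest eigenvalue is 0.003 with 2 of 40 extended (0.011 without EOT) and 0.009 with 10 or 20 of 40 (0.009 without).

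**3. Week 24 standard error of the difference.** Exact copy, 10 against 30 subjects:

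| Assumed profile | UN, no copy | AR(1), no copy | AR(1), with copy | Last against first |
|---|---|---|---|---|
| SD growing to 1 at Week 24 | 0.357 | 0.250 | 0.271 | −24% |
| Constant SD 1, lag-1 correlation 0.9 | 0.370 | 0.349 | 0.363 | −2% |
| Random slope with serial correlation, growing variance | 0.149 | not available | 0.108 | −28% |

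The percentages are 0.271/0.357 − 1, 0.363/0.370 − 1 and 0.108/0.149 − 1. In the two rows with the control column, the copy alone moves the AR(1) standard error by 0.021 and 0.014, towards the UN value. The rest of the gap is the AR(1) structure.

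**4. Overall LS means.** With equal weight per level, Week 24 carries 1/8 = 12.5% over eight visits. With an EOT level that repeats it, it carries 2/9 = 22.2%.

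**5. Other sources of convergence trouble.** The text says "The covariance structure will include a random intercept at the level of the subject to capture between-subject variability", on top of UN, while the UN code has no random intercept; the two together are not identifiable. In the 3/9 stratum there are 12 − 2 = 10 residual degrees of freedom, too few for UN over 14 visits even without EOT, but enough for eight.

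**The case against.** The best case for the plan is its own code. The ANTE(1) contrasts leave no room for EOT or EOS, and their count matches the eight scheduled visits to Week 24, the stated target. The wording also helps. The rule in SAP 2.3 follows a passage on choosing one record for descriptive tables and graphics, and SAP 5.2.1 speaks of results over time for the descriptive statistics but per time point for the MMRM. On that reading the copies were never meant for the model.

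This is good evidence of intent, but it does not specify the data. The contrasts appear only in the fallback calls. The planned UN call has no visit condition, and the inclusion rule is general with no exception stated. If eight visits are intended, Appendix 3 and SAP 2.3 disagree and nothing says which governs.

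A reader might infer that every subject's last value is bound to enter twice and that UN and ANTE(1) must fail. The documents do not support that. Entry into the model is one reading, and the failure depends on which visits are kept. Extension may also be common in the suppressed population, who enter with HBV DNA below 60 IU/mL (Protocol 4.1) and need below 200 IU/mL by Week 20 to continue (Protocol 6.1). In a Week 1 to 24 model their EOT would be a later value and not a copy of Week 24. Nor is EOT always Week 24 without extension: early stoppers, including the whole of Arm 1 once it was closed, have whichever on-treatment visit came last.

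**Conclusion.** The contradiction is real and should be removed. SAP 2.3, read with 5.2.1.1 and the UN call, admits the derived records; the fallback contrasts do not. If the records are admitted on unfiltered data, UN and ANTE(1) have unbounded likelihoods, ARH(1) with a random intercept can degenerate when the duplicate is exact, and AR(1) is the only listed structure that is clearly safe. The overall LS means would also be tilted towards the last value.

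A reader might infer that the copy distorts the Week 24 interval by a known amount. It does not. The range of about −2% to −28% rests on assumed variance profiles and compares two structures; the copy itself accounts for little of it. No reliable figure can be given for a stop at ARH(1), because its criterion has no maximum with an exact copy.

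The consequence is limited. The study is exploratory with no formal testing, and Protocol 11.3.1 makes the Bayesian comparison the primary-endpoint analysis and places the MMRM under Other Analyses (11.3.3). The Bayesian and dose-response analyses use Week 24 values only and are untouched. Severity is minor to moderate, and the point need not hold up the plan.

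**What to change.** State in SAP 2.3 and 5.2.1.1 that derived EOT and EOS records serve descriptive displays only and enter no repeated-measures model, whether for HBsAg, the other markers or the PRO scores. Add an explicit visit condition to all four calls in Appendix 3. For the primary Week 24 model this is `avisitn in (1,2,4,8,12,16,20,24)`, which agrees with the existing ANTE(1) contrasts; any model that runs beyond Week 24 should list its own time points. The filter also settles whether baseline (change zero for everyone), extension and follow-up records enter the primary model.

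The cost is two sentences and one condition per call. No information is lost, since every value behind EOT and EOS remains under its scheduled visit and in the descriptive tables.

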## **2.4. Missing and Partial data**

In general, missing data and partial dates will not be imputed and will be treated as missing. Only partially missing diagnosis and infection dates will be temporarily imputed to calculate the duration of infection and the time since diagnosis (see section 4.2.3). The original, non-imputed, dates will be listed.

To calculate the duration of infection or duration of diagnosis, if the reported date is partially missing, the imputation rules below is to be considered:

- Impute with the first day of the month if only day is missing
- Impute with January 1st if only the year is available
- Leave missing if completely missing

## **2.5. Definition of Subgroups**

The parameters below will be used as subgroup variable in the analysis where appropriate. Derivation will be described in section 4.2.2.

- Hepatitis B e Antigen (HBeAg) status at baseline
  - All
  - Positive
  - Negative
- Subject population
  - Currently not being treated

---

- Virologically suppressed by current NA treatment

Note: this should also be determined for all screened subjects.

- Hepatitis B Surface Antigen (HBsAg) level at baseline
  - For treatment naïve HBeAg positive (HBsAg  $\geq$ 10,000 IU/mL versus HBsAg  $<$ 10,000 IU/mL)
  - For all other (HBsAg  $\geq$ 1,000 IU/mL versus HBsAg  $<$ 1,000 IU/mL)
- Hepatitis B virus infection genotypes (coalesce)
  - Genotype A
  - Genotype B
  - Genotype C
  - Genotype D
  - Genotype E
  - Genotype F
  - Genotype G
  - Genotype H
  - Etc..
  - Unknown

## **2.6. Presentation of results**

Continuous parameters will be summarized using the following statistics: number of observations, mean, 95% confidence interval (CI) for mean, standard deviation (SD), standard error (SE), minimum, median and maximum, unless specified otherwise. The minimum and maximum will be presented to the same number of decimal places as the original data. The mean and median should be expressed with 1 decimal place more than the original values. The standard deviation, standard error and 95% confidence limits will be shown with 2 decimal place more than the original values.

Frequencies and percentages will be used for summarizing categorical (discrete) data. If a count is 0, the 0 count will be displayed, but the corresponding percentage should be omitted. If the corresponding denominator for the count is also 0, a hyphen (-) should be displayed rather than a 0 count or NAP [not applicable], and the corresponding percentage should be omitted.

---

All tables and graphs will be evaluated by subject population (i.e., subjects currently not being treated, virologically suppressed by current NA treatment or all population), by hepatitis B e antigen (HBeAg) status and overall, by treatment group (i.e., JNJ-56136379 [at two dose levels] and NA [entecavir {ETV} or tenofovir disoproxil fumarate {TDF}]) as monotherapy or coadministered), unless otherwise specified. Data will be presented in listings by subject population, HBeAg status, treatment group and subject number.

The main layout for the tables, unless specified otherwise, will be as followed:

Layout 1	Pooled Placebo + NA	JNJ6379 75 mg	JNJ6379 75 mg + NA	All JNJ6379 75mg	JNJ6379 250 mg	JNJ6379 250 mg + NA	All JNJ6379 250 mg	All JNJ6379 Doses

Layout 2	Pooled Placebo + NA	Placebo + NA Part A	Placebo + NA Part B

### **3. INTERIM ANALYSIS AND DATA REVIEW COMMITTEE**

#### **3.1. Interim Analysis**

At week 12 an interim analysis will be performed. The sponsor will remain blinded to the randomization codes (unless the Data Review Committee [DRC] recommends unblinded analyses) and data will be analyzed using dummy identification. Aggregated efficacy summary statistics (subsequent analyses) will be available to the sponsor at the blinded Week 12 interim analyses and the randomization codes will be available to the sponsor at the unblinded Week 24 interim analyses. The subjects and investigators will remain blinded to randomization codes until the end of the study. Note that blinding does not apply to the JNJ-56136379 monotherapy arms (open label).

The interim analyses, encompassing efficacy and safety, and pharmacokinetics, may be conducted for both **Parts A and B** when:

- at least 80% of subjects have completed visits at Week 12 or have discontinued earlier;
- at least 80% of subjects have completed visits at Week 24 or have discontinued earlier.
- at least 80% of subjects have completed visits at Week 48 or have discontinued earlier.

---

These interim analyses may also be performed separately by subject population (currently not being treated versus virologically suppressed) in case recruitment rates differ between the subject populations. Additional interim analyses (e.g., when subjects completed the Follow-up Week 12) may be performed at the sponsor's discretion to support decision making for further development of JNJ-56136379 and to support interactions with health authorities.

A final analysis will be performed when all subjects in the study have completed the Follow-up Week 24 visit or have discontinued earlier.

The selection of the required analyses output for the different types of interim analysis (e.g. Week 12, Week 24, Week 48, Final analysis) to be performed are indicated in the Data Presentation Specifications (DPS).

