
 
• To evaluate the frequency of sustained off-treatment response.
 
	
 
• Proportion of subjects with sustained reduction/suppression and/or sero-clearance considering single and multiple markers such as HBsAg, HBeAg, HBV DNA and ALT levels at FU Week 12, 24 and 48.
 

 
• To evaluate the frequency of virologic and clinical relapse after EOT.
 
	
 
• Proportion of subjects with virologic relapse defined as confirmed post-treatment increases in HBV DNA <math>>2,000</math> IU/mL after having met the treatment completion criteria.
 
• Proportion of subjects with clinical relapse defined as confirmed post-treatment increases in HBV DNA <math>>2,000</math> IU/mL after having met the treatment completion criteria, in association with confirmed ALT value <math>>2 \times</math> ULN.
 

 
• To evaluate the proportion of subjects requiring NA re-treatment during follow-up.
 
	
 
• Proportion of subjects who meet the re-treatment criteria as outlined in Section 6.4.
 

 
• To evaluate the efficacy of NA re-treatment during follow-up.
 
	
 
• Proportion of subjects with decline in HBV DNA, ALT and/or HBsAg levels after re-start of NA treatment during follow-up.
 

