**Part B:**

Part B (ie, Treatment Arms 6 to 10) will follow the same format as Part A, with a different dose of JNJ-56136379 (see [Figure 1](#)).

Randomization in each part will be stratified by:

- HBeAg status at screening (positive versus negative);
- HBsAg level at screening ( $\geq 10,000$  versus  $< 10,000$  IU/mL for HBeAg-positive subjects currently not being treated and  $\geq 1,000$  versus  $< 1,000$  IU/mL for all other subjects).

The aim is to have approximately 40% HBeAg-positive subjects who are currently not being treated and 30% HBeAg-positive virologically suppressed subjects. To this end, enrollment of HBeAg-negative subjects may be capped at 60% in subjects who are currently not being treated and at 70% in virologically suppressed subjects.

A DRC will be established for this study (see Section [11.12](#)) and will monitor safety and efficacy data in an unblinded manner on a regular basis throughout the study.

Part A will start first and will evaluate a 75-mg once-daily dose of JNJ-56136379. The dose to be administered in Part B will be 250 mg given once daily. This dose has been selected by the sponsor, in agreement with the DRC, based on all safety, PK, and antiviral activity data available following completion of the highest JNJ-56136379 dose group (who received 250 mg once

daily) in the Phase 1 study 56136379HPB1001 in treatment-naïve CHB-infected subjects treated for 28 days. (For a rationale on dose selection refer to the Study Design Rationale below.)

Each part of the study will consist of a screening phase (up to 8 weeks), a treatment phase (24 weeks or 48 weeks, depending on treatment response), and a post-treatment follow-up phase (24 weeks or 48 weeks, depending on treatment response). For an overview of the study design, see [Figure 1](#).

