For subjects who continue treatment in the extension phase:

- Subjects will be considered to have completed the study treatment if they have completed 48 weeks of study drug administration, after which they will discontinue JNJ-56136379 or placebo treatment. At Week 48:

- Subjects who meet all of the Individual Subject Treatment Completion Criteria (see Section 6.3) will complete all treatment. These subjects will be followed-up until 48 weeks after EOT (Schedule 2). If, during the 48-week follow-up, a subject meets one of the re-treatment criteria described in Section 6.4, NA treatment (ETV or TDF) should be re-started.
- Subjects who do not meet the Individual Subject Treatment Completion Criteria should start (in case of JNJ-56136379 monotherapy, ie, Treatment Arms 1 and 6) or continue (in case NA treatment was part of the assigned study treatment, ie, Treatment Arms 2 to 5 and 7 to 10) NA treatment as per local treatment guidelines. These subjects will be followed-up until 24 weeks after the end of study treatment (Schedule 1).
- Subjects will be considered to have completed the study if they have completed the assessments of the end of study visit (FU Week 24 [Schedule 1] or FU Week 48 [Schedule 2]).
- For subjects who do not meet the Individual Subject Treatment Completion Criteria and do not start or continue NA treatment at Week 48, an additional 24-week follow-up (as per local treatment guidelines) by their primary care physician, outside of the study, is recommended after study completion.

The duration of individual participation will be up to approximately 56 weeks (subjects not eligible to continue treatment in the extension phase), up to 80 weeks (subjects continuing treatment in the extension phase but not meeting the treatment completion criteria), or up to 104 weeks (subjects meeting treatment completion criteria).

Efficacy will be evaluated through different measures (see Section 9.2).

Samples for HBV genome sequence will be taken at the time points indicated in the **TIME AND EVENTS SCHEDULE** (see Section 9.3). Sequencing of baseline samples will be performed by default if HBV DNA levels are within the ranges required for the sequencing assay. The sequencing of samples obtained after baseline may be triggered by the sponsor virologist based on changes in HBV DNA levels observed in each individual subject and the limits of the sequencing assay.

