## **11.11. Interim Analyses**

At the Week 12 interim analyses, the sponsor study team will remain blinded to the randomization codes (unless the DRC recommends unblinded analyses, see below) and data will be analyzed using dummy identification and aggregated efficacy summary statistics. At the unblinded Week 24 interim analyses (and subsequent analyses), the sponsor study team members involved in safety monitoring of the treatment extension phase as well as the investigator, site personnel and subjects will remain blinded. The sponsor study team members involved in safety monitoring of the treatment extension phase will remain blinded to the treatment/randomization codes until the end of the treatment extension phase while the investigator, site personnel and

subjects will remain blinded until the end of the study. Note that blinding does not apply to the JNJ-56136379 monotherapy arms.

Interim analyses, encompassing efficacy, safety, and pharmacokinetics, may be conducted for **Part A** and **Part B** at study Week 12, 24, 36, 48 and 72 separately when at least 80% of subjects have completed the respective visit (ie, Week 12, Week 24 for all subjects, FU Week 12/Week 36 and FU Week 24/Week 48 for subjects receiving 24/48 weeks of study treatment, and, FU Week 24 for subjects receiving 48 weeks of study treatment, respectively) or have discontinued earlier (see also [Figure 1](#)).

At the sponsor's discretion, these interim analyses may also be performed separately by subject population (currently not being treated versus virologically suppressed) in case recruitment rates differ between the subject populations.

Additional interim analyses may be performed at the sponsor's discretion to support decision making for further development of JNJ-56136379 and to support interactions with health authorities.

A final analysis will be performed when all subjects in the study have completed the last study-related follow-up visit or have discontinued earlier.

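### SAP Section 3.1 sets the final analysis at Follow-up Week 24, against the protocol's last follow-up visit, so complete Follow-up Week 48 off-treatment data are not guaranteed

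*SAP*

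**What the plan says.** The SAP, Section 3.1, fixes the trigger at one visit for everyone: "A final analysis will be performed when all subjects in the study have completed the Follow-up Week 24 visit or have discontinued earlier".

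The protocol, Section 11.11 (repeated in the synopsis), ties it to each subject's own last visit: "A final analysis will be performed when all subjects in the study have completed the last study-related follow-up visit or have discontinued earlier". The same section treats FU Week 24 after 48 weeks of treatment as an optional interim analysis, at study Week 72.

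The last visit differs by follow-up schedule. Schedule 1 ends at FU Week 24. For subjects who meet all treatment completion criteria at the end of the extension, protocol Section 3.1 says: "These subjects will be followed-up until 48 weeks after EOT (Schedule 2". Among the extension-phase endpoints, protocol Section 2.1 lists sustained off-treatment response judged on "HBsAg, HBeAg, HBV DNA and ALT levels at FU Week 12, 24 and 48". Virologic relapse, clinical relapse and NA re-treatment after meeting the completion criteria stand in the same table.

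Other parts of the SAP presuppose the full 48 weeks. Section 1.1 takes its objectives from protocol Section 2.1. Table 2 has windows for FU Weeks 32, 40 and 48. Appendix 7 reproduces Schedule 2 with FU Week 48 as the end-of-study visit. Table 1 and its note end the last phase at trial termination and provide for a data cut-off only at an interim or DRC analysis.

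**The concern.** The two governing documents disagree on when the trial's data become final. The SAP trigger can be met while Schedule 2 subjects are still being followed off treatment, and the SAP specifies nothing after it. The protocol endpoint at FU Week 48 then has no analysis that is certain to contain complete data.

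The Schedule 2 group is the trial's evidence on finite treatment: who stays controlled after stopping everything, who relapses, and who needs NA again. A cumulative relapse proportion depends on length of follow-up. If some subjects are counted after 24 weeks and others after 48, the proportion mixes two risk periods and misses any relapse after the cut.

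**Working it through.** **1. Reproduce the protocol's own durations.** Inputs from protocol Section 3.1: screening up to 8 weeks, treatment 24 or 48 weeks, follow-up 24 or 48 weeks.

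- 24 weeks of treatment, Schedule 1: 8 + 24 + 24 = 56 weeks (stated: 56)
- 48 weeks of treatment, Schedule 1: 8 + 48 + 24 = 80 weeks (stated: 80)
- 48 weeks of treatment, Schedule 2: 8 + 48 + 48 = 104 weeks (stated: "or up to 104 weeks (subjects meeting treatment completion criteria")

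All three agree, so FU Week 48 is the last visit for Schedule 2.

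**2. Check the SAP's follow-up days.** Table 2 sets the target day at the protocol day minus 5, that is 7 × week − 5. FU Week 24: 168 − 5 = 163. FU Week 48: 336 − 5 = 331. Both match the table. The distance is 331 − 163 = 168 days, or 24 weeks.

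**3. What each trigger guarantees for one Schedule 2 subject.**

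- SAP trigger: data to study Week 48 + 24 = 72.
- Protocol trigger: data to study Week 48 + 48 = 96.
- Largest shortfall: 96 − 72 = 24 of 48 off-treatment weeks.
- Schedule 2 visits are FU Weeks 2, 4, 6, 8, 12, 16, 20, 24, 32, 40 and 48. Three of the 11 (32, 40, 48) fall after FU Week 24.

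**4. How many subjects could be affected.** The documents do not give the accrual period R. As an illustration, assume uniform accrual over R weeks, the same chance of entering Schedule 2 throughout, and a last-enrolled subject treated for 48 weeks. The trigger is then met at R + 72 weeks after the first enrolment. A Schedule 2 subject enrolled at week t reaches FU Week 48 at t + 96, and is incomplete if t + 96 > R + 72, that is t > R − 24. The incomplete share is 24/R, capped at 1.

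| R (weeks, assumed) | Share of Schedule 2 lacking FU Week 48 |
|---|---|
| 24 | 100% |
| 40 | 60% |
| 52 | 46% |
| 78 | 31% |
| 104 | 23% |

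**5. How the SAP would classify those subjects.** The relapse definitions are in the parameter definitions under SAP Section 5.3.

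- *Viral and biochemical relapse.* The code for no relapse but still ongoing is limited to interim analyses. At a final analysis, an assessable subject with at least one post-treatment value and no relapse fits only the plain No code. The secondary analysis text takes Yes plus No as the viral relapse denominator, so this subject counts as a completed non-relapser.
- *Clinical viral relapse.* The No code requires that the subject is not ongoing, and the ongoing code is again interim-only. A subject still in follow-up fits neither.
- *No correction by censoring.* Relapse is not among the time-to-event variables in Table 5.
- *Partial offset.* A relapse criterion met at the last observed time point counts as confirmed, so a single high value at the cut would be counted.
- *Response at FU Week 48.* SAP Section 2.4 does not impute missing data in general. A subject who has not reached the visit is simply missing there.

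**The case against.** The strongest reply is that the trigger needs **all** subjects in both parts to reach FU Week 24 or discontinue. Part A started first, and its Schedule 2 subjects, like others enrolled early, may have reached FU Week 48 by then. This stands. A reader might infer from the SAP sentence that the FU Week 48 endpoints will necessarily be analysed incomplete. The documents do not support that: Week 72 against Week 96 is the worst case for one subject, not a cut date for the study, and the number incomplete could be small or zero.

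A second reply is that Table 1 provides no cut-off for a final analysis and the FU Week 48 windows remain, so the sentence is probably a leftover. The SAP does carry other superseded text, such as a high dose still to be determined and extension at HBV DNA below LLOQ. That explains the sentence but does not settle which trigger applies, and it adds an internal contradiction to the one with the protocol.

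Third, a reader might infer that sustained response at FU Week 48 would be biased upwards. That is not shown. Subjects not yet at the visit are missing because they enrolled late, which mainly costs precision. The case for bias rests on cumulative relapse. Even there it is not airtight, because SAP Section 3.1 names the final analysis in its examples of interim analysis types, so a programmer might still apply the ongoing code.

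Finally, the study is exploratory, these endpoints are listed apart from the primary and secondary ones, and Schedule 2 visits continue under the protocol whatever the SAP says. All of this is fair and limits the severity.

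**Conclusion.** The contradiction is real and unreconciled. Under the SAP trigger, completeness of the FU Week 48 off-treatment endpoints is not guaranteed. A later-enrolled Schedule 2 subject could lack up to 24 of 48 off-treatment weeks and 3 of 11 visits. The affected share depends on accrual; under the uniform-accrual assumptions above it runs from 23% (R = 104) to 100% (R = 24), and other patterns could bring it to zero.

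Read literally, the coding rules could understate cumulative viral relapse and leave clinical relapse without a valid code for subjects still in follow-up. Response at FU Week 48 would mainly lose precision, and response at FU Weeks 12 and 24 is untouched.

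The Week 24 primary endpoint and every Schedule 1 subject are unaffected. The point should be fixed, but it does not threaten the trial's main result.

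**What to change.** Replace the sentence in SAP Section 3.1 with the protocol's trigger: the final analysis takes place once every subject has had the last study-related follow-up visit (FU Week 24 on Schedule 1, FU Week 48 on Schedule 2) or has discontinued earlier. Label any FU Week 24 cut after 48 weeks of treatment as the protocol's Week 72 interim analysis. The interim-only ongoing codes and the cut-off rule in Table 1 then work as written.

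The cost is one SAP sentence and one label. No visits or data are added. The final report may come up to 24 weeks later than under the present SAP wording, which is the timing the protocol already plans.
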